#### 4.4.2.5. Analyses Related to PASI

##### Through Week 24

- The change and percent change from baseline in PASI total score will be summarized over time through Week 24 by treatment group.
- The proportions of PASI responses (PASI 75, PASI 90, and PASI 100) will be summarized over time through Week 24 by treatment group.
- The proportions of participants achieving  $\geq 75\%$  improvement,  $\geq 90\%$  improvement, or achieving 100% improvement from baseline in PASI disease component (Induration, Erythema, and Scaling) and region component (head, trunk, upper extremities, and lower extremities) at Week 16 will be summarized by treatment group.

##### From Week 24 Through Week 52 – Randomized Withdrawal and Retreatment Period

###### Randomized Withdrawal period

- The Life table method will be used to estimate the distribution of time to loss of  $\geq 50\%$  of the Week 24 PASI improvement (i.e., time to retreatment) after withdrawal. The median time to loss of  $\geq 50\%$  of the Week 24 PASI improvement will be provided.
- The proportion of PASI responses (PASI 75, 90, and 100) will be summarized over time from Week 24 through Week 52 for participants randomized at Week 24.
- The change and percent change from baseline in PASI total score will be summarized over time from Week 24 through Week 52 for participants randomized at Week 24.

###### Retreatment period

- The change and percent change from baseline in PASI total score will be summarized at the time of retreatment and over time (e.g., 4 weeks after retreatment, 8 weeks after retreatment, 12 weeks after retreatment).
- The PASI responses (PASI 75, 90 and 100) with respect to baseline will be summarized over time (e.g., 4 weeks after retreatment, 8 weeks after retreatment, 12 weeks after retreatment) following retreatment with JNJ-77242113.

**Through Week 52 – Non-randomized JNJ-77242113 Treatment**

- The change and percent change from baseline in PASI will be summarized over time by treatment group.
- The proportion of PASI responses (PASI 75, 90, and 100) will be summarized over time by treatment group.
- The proportion of participants who achieve a PASI 75 response at Week 52 will be summarized among adolescent participants who were randomized to JNJ-77242113 at Week 0 and were PASI 75 responders at Week 24.
- The proportion of participants who achieve a PASI 90 response at Week 52 will be summarized among adolescent participants who were randomized to JNJ-77242113 at Week 0 and were PASI 90 responders at Week 24.

**From Week 64 Through Week 156**

- The change and percent change from baseline in PASI total score will be summarized over time.
- The proportion of PASI responses (PASI 75, 90, and 100) will be summarized over time based on mNRI and observed data after accounting for ICE 1.

**4.4.2.6. Analyses Related to IGA****Through Week 24**

- The proportions of IGA responses (IGA 0, IGA 0 or 1) will be summarized over time through Week 24 by treatment group.

**From Week 24 Through Week 52 – Randomized Withdrawal and Retreatment Period**Randomized Withdrawal period

- The proportion of IGA responses (IGA 0, IGA 0 or 1) will be summarized over time through Week 52 for participants randomized at Week 24.

Retreatment period

- IGA scores at the time of retreatment of JNJ-77242113 and the proportion of retreated participants who achieve an IGA 0, and an IGA 0 or 1 responses over time (e.g., 4 weeks after retreatment, 8 weeks after retreatment, 12 weeks after retreatment) following the retreatment of JNJ-77242113 will be summarized for participants randomized at Week 24.

**Through Week 52 – Non-randomized JNJ-77242113 Treatment**

- The proportion of IGA responses (IGA 0, and IGA 0 or 1) will be summarized over time by treatment group.
- The proportion of participants who achieve an IGA 0 or 1 response at Week 52 will be summarized among adolescent participants who were randomized to JNJ-77242113 at Week 0 and were IGA 0 or 1 responders at Week 24.

**From Week 64 Through Week 156**

- The proportion of IGA responses (IGA 0, and IGA 0 or 1) will be summarized over time based on mNRI and observed data after accounting for ICE 1.

**4.4.2.7. Analyses Related to ss-IGA****Through Week 24**

- The proportion of ss-IGA responses (ss-IGA score of 0, ss-IGA score 0 or 1 and at least a 2-grade improvement from baseline) will be summarized through Week 24 by treatment group among participants with a baseline ss-IGA score  $\geq 2$  and  $\geq 3$  respectively. In addition, the proportion of ss-IGA score of 0 will be compared between treatment groups at Week 16 among participants with a baseline ss-IGA score  $\geq 2$  and  $\geq 3$  respectively. The proportion of ss-IGA score of 0 or 1 will be compared between treatment groups at Week 16 among participants with a baseline ss-IGA score  $\geq 3$ .

**4.4.2.8. Analysis Related to Static Physician's Global Assessment of Genitalia****Through Week 24**

- The proportion of sPGA-G responses (sPGA-G score of 0, sPGA-G score 0 or 1 and at least a 2-grade improvement from baseline) will be summarized through Week 24 among participants with an sPGA-G score  $\geq 2$  and  $\geq 3$  at baseline respectively. In addition, the proportion of sPGA-G score of 0 will be compared between treatment groups at Week 16 among participants with a baseline sPGA-G score  $\geq 2$  and  $\geq 3$  respectively. The proportion of sPGA-G score of 0 or 1 will be compared between treatment groups at Week 16 among participants with a baseline sPGA-G score  $\geq 3$ .

**4.4.2.9. Analysis Related to Physician's Global Assessment of Hands and/or Feet****Through Week 24**

- The proportion of hf-PGA responses (hf-PGA score of 0, hf-PGA score of 0 or 1 and at least a 2-grade improvement from baseline) will be summarized through Week 24 among participants with a baseline hf-PGA score  $\geq 2$  and  $\geq 3$  respectively. In addition, the proportion of hf-PGA score of 0 will be compared between treatment groups at Week 16 among participants with a baseline hf-PGA score  $\geq 2$  and  $\geq 3$  respectively. The proportion of hf-PGA score of 0 or 1 will be compared between treatment groups at Week 16 among participants with a baseline hf-PGA score  $\geq 3$ .

**4.4.2.10. Analysis Related to Fingernail Physician's Global Assessment****Through Week 24**

- The proportion of f-PGA responses (f-PGA score of 0, and f-PGA score of 0 or 1) will be summarized through Week 24 by treatment group among participants with a baseline f-PGA score  $\geq 2$ . In addition, the proportion of f-PGA score of 0 will be compared between treatment groups at Week 16 among participants with a baseline f-PGA score  $\geq 2$ .

#### **4.4.2.11. Analysis Related to Modified Nail Psoriasis Area and Severity Index Through Week 24**

- The percent change from baseline in mNAPSI will be summarized through Week 24 by treatment group for participants with a baseline mNAPSI score  $>0$ .

#### **4.4.2.12. Analysis Related to PGA of Disease Activity (adolescent) Through Week 52**

- The change from baseline in PGA disease activity score will be summarized through Week 52 by treatment group among adolescent participants with a previous diagnosis of PsA at or before screening.

#### **4.4.2.13. Analyses Related to Psoriasis Symptom and Sign Diary Through Week 24**

- The change from baseline in PSSD symptom score and sign score will be summarized over time through Week 24 by treatment group.
- The proportions of participants who achieve a PSSD symptom score of 0 and sign score of 0 will be summarized over time through Week 24 among participants with a baseline PSSD symptom score  $>0$ , and baseline sign score  $>0$  respectively by treatment group. Additionally, these endpoints will be summarized over time by treatment group and age group.
- The proportion of participants who achieve a  $\geq 4$ -point improvement from baseline in PSSD itch score will be summarized over time through Week 24 among participants with baseline PSSD itch score  $\geq 4$ . Additionally, this endpoint will be summarized over time by treatment group and age group.
- The change from baseline in each PSSD individual scale score will be compared between treatment groups at Week 16.

#### **Through Week 52 – adolescent**

- The change from baseline in PSSD symptom score and sign score will be summarized over time through Week 52 by treatment group among adolescent participants.
- The proportion of participants who achieve a PSSD symptom score of 0, sign score of 0, and  $\geq 4$ -point improvement from baseline in PSSD itch score will be summarized over time through Week 52 by treatment group among adolescent participants with a baseline PSSD symptom score  $>0$ , baseline sign score  $>0$ , and baseline PSSD itch score  $\geq 4$  respectively.

#### **From Week 64 Through Week 156**

- The change from baseline in PSSD symptom score and sign score will be summarized over time.
- The proportion of participants who achieve a PSSD symptom score of 0, sign score of 0, and  $\geq 4$ -point improvement from baseline in PSSD itch score will be summarized over time among participants with a baseline PSSD symptom score  $>0$ , and baseline sign score  $>0$ , and baseline PSSD itch score  $\geq 4$  respectively.

**4.4.2.14. Analyses Related to DLQI (adult) and CDLQI (adolescent)****Through Week 24**

- The change from baseline in DLQI score will be summarized over time through Week 24 by treatment group among adult participants.
- The change from baseline in CDLQI will be summarized over time through Week 24 by treatment group among adolescent participants.
- The proportion of participants with DLQI score of 0 or 1 will be summarized over time through Week 24 by treatment group among adult participants with a baseline DLQI score >1.
- The proportion of participants with CDLQI score of 0 or 1 will be summarized over time through Week 24 by treatment group among adolescent participants with a baseline CDLQI score >1.

**Through Week 52 – adolescent**

- The change from baseline in CDLQI will be summarized over time by treatment group among adolescent participants.
- The proportion of participants with CDLQI score of 0 or 1 will be summarized over time among the adolescent participants with a baseline CDLQI score >1.

**From Week 64 Through Week 156**

- The change from baseline in DLQI score will be summarized over time among adult participants.
- The change from baseline in CDLQI will be summarized over time among adolescent participants.
- The proportion of participants with DLQI score of 0 or 1 will be summarized over time among the adult participants with a baseline DLQI score >1.
- The proportion of participants with CDLQI score of 0 or 1 will be summarized over time among the adolescent participants with a baseline CDLQI score >1.

**4.4.2.15. Analysis Related to Adult Genital Psoriasis Sexual Frequency Questionnaire (GenPs-SFQ) (adult)****Through Week 24**

- The proportion of participants with a GenPs-SFQ item 2 score of 0 at Week 16 will be compared between the JNJ-77242113 group and placebo among adult participants with a baseline GenPs-SFQ item 2 score  $\geq 2$  and a baseline sPGA-G score  $\geq 3$ .
- The proportion of participants with a GenPs-SFQ item 2 score of 0, and score of 0 or 1 at Week 16 will be compared between the JNJ-77242113 group and placebo among adult participants with a baseline GenPs-SFQ item 2 score  $\geq 2$  and a baseline sPGA-G score  $\geq 2$ .
- The GenPs-SFQ item 2 score of 0 and score of 0 or 1 will be summarized over time through Week 24 by treatment group among adult participants with a baseline GenPs-SFQ item 2 score  $\geq 2$  and a baseline sPGA-G score  $\geq 3$ .

- The GenPs-SFQ item 2 score of 0 and score of 0 or 1 will be summarized over time through Week 24 by treatment group among adult participants with a baseline GenPs-SFQ item 2 score  $\geq 2$  and a baseline sPGA-G score  $\geq 2$ .

#### **4.4.2.16. Analyses Related to PROMIS-29 (adult) and PROMIS-25 (adolescent) Through Week 24**

- The change from baseline in PROMIS-29 domain scores, Physical Component Score (PCS), and Mental Component Score (MCS) will be summarized through Week 24 by treatment group among adult participants.
- The change from baseline in PROMIS-25 domain scores will be summarized through Week 24 by treatment group among adolescent participants.

#### **Through Week 52 – adolescent**

- The change from baseline in PROMIS-25 domain scores will be summarized over time by treatment group among adolescent participants.

#### **From Week 64 Through Week 156**

- The change from baseline in PROMIS-29 PCS and MCS will be summarized over time among adult participants.
- The change from baseline in PROMIS-25 domain scores will be summarized over time among adolescent participants.

#### **4.4.2.17. Analysis Related to PsA Pain Assessment**

##### **Through Week 24**

- The change from baseline in PsA pain will be summarized at Week 8 and Week 16 by treatment group among participants with a diagnosis of PsA at or before screening.

##### **Through Week 52 – adolescent**

- The change from baseline in PsA pain will be summarized through Week 52 by treatment group among adolescent participants with a diagnosis of PsA at or before screening.

#### **4.4.2.18. Analysis Related to PsA Disease Activity**

##### **Through Week 24**

- The change from baseline in PsA disease activity will be summarized at Week 8 and Week 16 by treatment group among participants with a diagnosis of PsA at or before screening.

##### **Through Week 52 – adolescent**

- The change from baseline in in PsA disease activity will be summarized through Week 52 by treatment group among adolescent participants with a diagnosis of PsA at or before screening.

#### **4.4.2.19. Analysis Related to Acceptability and Palatability (Adolescent) Through Week 16**

- The acceptability and palatability (e.g. sweetness, bitterness, overall, and swallowability) will be summarized at Week 0 and Week 16 by treatment among adolescent participants.

#### **4.5. Safety Analyses**

All safety analyses will be performed using safety analysis set based on actual intervention received. No formal statistical comparison is planned.

For all continuous safety variables, descriptive statistics by intervention group will include the N, mean, standard deviation, median, minimum, and maximum. Categorical variables will be summarized by intervention group using frequency counts and percentages.

The cumulative safety data will be analyzed through different study periods as shown below. Unless otherwise specified, tabular summaries of safety events are also presented as following:

##### **Summary through Week 16:**

- Placebo
- JNJ-77242113

##### **Summary through Week 24:**

- Placebo → JNJ-77242113
- JNJ-77242113

For participants who were randomized to placebo at Week 0 and discontinued treatment prior to Week 16, the safety events/measurements occurred after Week 16 will be provided in a listing.

##### **Summary through Week 52 and /or through the reporting period (approximately the date when last participant finishing Week 52 visit):**

Safety data will be summarized by intervention group defined as follows:

- Placebo → JNJ-77242113: all participants who were randomized to placebo at Week 0, and later crossed over to receive treatment with JNJ-77242113 at or after Week 16. Only the safety events/measurements from these participants that occurred at or after Week 16 will be included.
- JNJ-77242113: Participants who were randomized to JNJ-77242113 at Week 0 and were treated with JNJ-77242113. All the safety events/measurements from these participants that occurred at or after Week 0 administration will be included in this group. However, safety events that occurred during the withdrawal period (on and after Week 28 and before retreatment) may be excluded for participants who were rerandomized to placebo at Week 24.
- Combined JNJ-77242113: all participant as described above in the Placebo → JNJ-77242113 and the JNJ-77242113 groups.

In addition, selected safety analysis from Week 24 through Week 52 may be performed among participants who were randomized to either receive placebo or continue to receive JNJ-77242113 at Week 24.

- Placebo (withdrawal): Participants who were randomized to JNJ-77242113 at Week 0, were PASI 75 or IGA 0 or 1 responders at Week 24, and rerandomized to placebo group at Week 24. Only the safety events/measurements from these participants that occurred at or after Week 24 randomization and before retreatment with JNJ-77242113 will be included in this group.
- Placebo → retreatment: Participants who were randomized to placebo at Week 24, started treatment with placebo, and retreated with JNJ-77242113 upon loss of 50% Week 24 PASI improvement. Only the safety events that occurred at or after their first retreatment of JNJ-77242113 will be included in this group.
- Placebo (combined 1 and 2 above): Participants who were randomized to placebo at Week 24. All safety events/measurements from these participants that occurred at or after Week 24 randomization will be included.
- JNJ-77242113 (Rerandomization): Participants who were randomized to JNJ-77242113 at Week 24 and continue to receive treatment with JNJ-77242113. All safety events occurred at or after Week 24 rerandomization will be included in this group.

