Randomization		X							X							Randomization at W24 is rerandomization for adult participants receiving JNJ-77242113 from W0 to W24.
Dispense study intervention		X	X	X	X	X	X	X	X	X	X	X	X	X		Dispense study intervention after all other procedures. Study intervention may also be dispensed between visits.
Administer study intervention		Oral study intervention will be self-administered daily (Section 6.1).														Study intervention will be taken at the site during the baseline (W0), W4, and W16 visits, where both a pre- and post-dose PK sample will be drawn. At W16 study intervention will be

Period	Screening	Placebo-controlled					JNJ-77242113 Treatment		Randomized withdrawal and retreatment						Unscheduled ^{a,b}	Notes: See Section 1.3.2 for Early Termination Visit procedures.
Week (W)	-5-0	0	2	4	8	12	16	20	24	28	32	36	44	52		
Visit Window (days)			±2	±2	±4	±4	±4	±4	±4	±4	±4	±4	±4	±4		
Study Procedure																
																taken from a newly dispensed drug blister pack at the visit.
Study intervention accountability			X	X	X	X	X	X	X	X	X	X	X	X	X	
Efficacy Assessments																
PROs: Complete in the order shown before any tests, procedures, or consultations for all visits unless otherwise noted.																
PSSD (24-hour recall)	Daily Diary beginning at Screening through W16.															
PSSD (7-day recall)							X	X	X	X	X	X	X	X	X	
DLQI or CDLQI		X	X	X	X	X	X	X	X	X	X	X	X	X	X	
GenPs-SFQ		X			X		X		X			X		X		W8-W52: Collect only for participants with active genital psoriasis at W0. Only for participants ≥18 years of age.
PROMIS-29 or PROMIS-25		X			X		X		X			X		X		PROMIS-25 is only for participants <18 years of age.
TSQM-E							X							X		Effectiveness domain only (Section 8.2.10.7).
EQ-5D-5L		X			X		X		X			X		X		
PsA Pain Assessment		X			X		X							X		W8-W52: Collect only for participants with a diagnosis of PsA at or before screening.
PsA Disease Activity Assessment		X			X		X							X		
Acceptability and palatability assessment		X					X									Only for participants <18 years of age.
ClinROs																
IGA	X	X	X	X	X	X	X	X	X	X	X	X	X	X	X	
PASI	X	X	X	X	X	X	X	X	X	X	X	X	X	X	X	
BSA	X	X	X	X	X	X	X	X	X	X	X	X	X	X		

Period	Screening	Placebo-controlled					JNJ-77242113 Treatment		Randomized withdrawal and retreatment						Unscheduled ^{a,b}	Notes: See Section 1.3.2 for Early Termination Visit procedures.
Week (W)	-5-0	0	2	4	8	12	16	20	24	28	32	36	44	52		
Visit Window (days)			±2	±2	±4	±4	±4	±4	±4	±4	±4	±4	±4	±4		

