8.3.6. Suicidal Ideation and Behavior Risk Monitoring

The C-SSRS defines 5 subtypes of suicidal ideation and 4 possible suicidal behaviors, as well as non-suicidal self-injurious behavior and completed suicide. It will be used as a screening tool to prospectively evaluate suicidal ideation and behavior in this study, as part of a comprehensive evaluation of safety.

Two versions of it will be used in this study: the ‘Baseline/Screening’ version of the C-SSRS will be conducted during the screening visit and the ‘Since Last Visit’ version of the C-SSRS will be completed at Week 0 and all other visits through the end of the study.

The investigator or trained study-site personnel will interview the participant in a private place and complete the C-SSRS on the eCOA device. At the conclusion of each assessment, the trained personnel administering the C-SSRS will determine the level of suicidal ideation or behavior, if any. They will then determine the next course of action if any level of suicidal ideation or behavior is reported. The participant should not be released from the site until the C-SSRS has been reviewed by the investigator and the participant’s risk has been assessed and follow-up determined, as appropriate.

For each assessment after Week 0, the following actions should be taken, if applicable:

- No suicidal ideation or behaviors (including self-injurious behavior without suicidal intent): No further action is needed.
- Suicidal ideation levels 1-3 or non-suicidal self-injurious behavior: Participant risk is assessed by the investigator.
- Suicidal ideation levels 4 or 5 or any suicidal behavior: Participant risk assessed and referral to a mental health professional.

Any C-SSRS finding, which in the opinion of the investigator is new or considered to be a worsening and clinically significant, should be reported on the AE eCRF.

In addition, caregivers of the participants will be instructed to immediately report any suicidal ideation, suicidal behavior, or suicide attempt to the investigator.

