#### 4.5.3.3. Columbia-Suicide Severity Rating Scale

The C-SSRS will be used as a screening tool to prospectively evaluate suicidal ideation and behavior among study participants. The C-SSRS defines 5 subtypes of suicidal ideation and 4 possible suicidal behaviors, as well as non-suicidal self-injurious behavior and completed suicide.

Two versions of the C-SSRS will be used in this study, the *Baseline/Screening* version and the *Since Last Visit* version. The *Baseline/Screening* version will be conducted during the screening visit and the *Since Last Visit* version will be conducted at all other visits.

The following are C-SSRS categories and have binary responses (yes/no). A “yes” response to any C-SSRS category will be assigned a score as below:

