##### Suicidal Behavior (6-10)

6=Preparatory Acts or Behavior

7=Aborted Attempt

8=Interrupted Attempt

9=Actual Attempt (non-fatal)

10=Completed Suicide

If no events qualify for a score of 1 to 10, a score of 0 will be assigned (0 = “Negative result [no suicidal ideation or behavior]”). Higher scores indicate greater severity.

Suicidal ideation and behavior will be summarized by C-SSRS categories and intervention group based on the most severe/maximum post baseline C-SSRS outcome or AE of suicidal ideation, suicidal behavior excluding completed suicide, or completed suicide through Week 16, through Week 24, through the reporting period at Week 52 DBL, and through Week 160. The baseline is defined as the most severe/maximum C-SSRS score at either screening or Week 0.

The maximum score assigned for each participant will also be summarized into one of three broad categories: No suicidal ideation or behavior, suicidal ideation, and suicidal behavior. A shift table for change in C-SSRS categories of no suicidal ideation or behavior, suicidal ideation, and suicidal

behavior from baseline through Week 16, through 24, through reporting period of Week 52 DBL, and through Week 160 will be presented, where the baseline category is based on C-SSRS score and the post baseline is based on C-SSRS or AE data.

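### In the through-Week-52 safety summary, the Week 16 suicidality interview of placebo crossovers recalls placebo weeks but counts as JNJ-77242113 data

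*SAP*

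**What the plan says.** SAP 4.5 opens with a general principle: "All safety analyses will be performed using safety analysis set based on actual intervention received". It then defines columns period by period. In the summary through Week 52 or the reporting period, the Placebo → JNJ-77242113 column holds participants who started on placebo and later crossed over, with this window: "Only the safety events/measurements from these participants that occurred at or after Week 16 will be included". The Combined JNJ-77242113 column takes in the same participants.

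Two neighboring groups in that summary start at a dose. For participants randomized to JNJ-77242113 at Week 0: "All the safety events/measurements from these participants that occurred at or after Week 0 administration will be included in this group". For withdrawn participants who are retreated: "Only the safety events that occurred at or after their first retreatment of JNJ-77242113 will be included in this group".

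On the C-SSRS, Protocol 8.3.6 says that the Since Last Visit "version of the C-SSRS will be completed at Week 0 and all other visits through the end of the study", and SAP 4.5.3.3 agrees that after screening this "version will be conducted at all other visits". SAP 4.5.3.3 tabulates each participant by C-SSRS category and intervention group "based on the most severe/maximum post baseline C-SSRS outcome" or related AE. One of its reporting periods ends at the Week 52 database lock. Baseline is the worse of screening and Week 0, with no reset at crossover.

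On the order of a visit, the Schedule of Activities (Protocol 1.3.1) says "Dispense study intervention after all other procedures". It also has the Week 16 dose taken on site from a pack handed out that day.

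**The concern.** A column headed JNJ-77242113 should describe what happened on the drug. A recall instrument needs two conditions for that: the interview must come after the first dose, and the period it asks about must also come after the first dose. The Week 16 interview of a crossover participant fails the second condition whatever the order of procedures that day, because it asks about Weeks 12 to 16, when the participant took placebo.

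The summary takes the worst post-baseline finding, so one record can set a participant's category. If such findings are sparse, one misplaced record visibly changes the reported figure. Suicidality is also closely watched in this trial: the protocol has C-SSRS exclusion criteria (5.2) and stopping criteria (7.1.3), and it reports a suicide attempt among the Phase 2b discontinuations (2.2).

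**Working it through.** The plan states no figure on this point, so there is none to reproduce. The check follows one crossover participant through the rules and then counts.

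**Tracing the Week 16 interview**

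1. Treatment: placebo from Week 0 to Week 16, then JNJ-77242113 (Protocol 4.1).
2. Visits: the C-SSRS is done at every visit, and the visit before Week 16 is Week 12 (Protocol 1.3.1).
3. Recall: Since Last Visit, so Weeks 12 to 16, all on placebo. If Week 12 was missed, the recall is longer and still all placebo.
4. Window: the interview falls at Week 16, so the SAP 4.5 rule admits it to both JNJ columns.
5. Status: baseline stays at screening/Week 0, so Week 16 is post-baseline and enters the worst-category rule.
6. Exclusions: neither SAP 4.5 nor 4.5.3.3 removes it.

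**Share of the data (crossover participant attending every visit to Week 52)**

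- Interviews in the window: Weeks 16, 20, 24, 28, 32, 36, 44, 52 = 8. Placebo share = 1/8 = 12.5%.
- Recalled weeks: 52 − 12 = 40, of which 16 − 12 = 4 are placebo. Share = 4/40 = 10%.
- With the window moved to after the first dose visit: 7 interviews recalling 52 − 16 = 36 weeks, none on placebo.

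These shares are ceilings for such participants. The C-SSRS table runs to the reporting period of the Week 52 lock, which is roughly when the last participant finishes Week 52. Earlier enrollees therefore add later visits. With Week 64 included, the shares fall to 1/9 = 11.1% and 4/(64 − 12) = 4/52 = 7.7%.

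**Effect of one misassigned participant (planned numbers, SAP Section 5: 400 and 200)**

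- Crossover column: 1/200 = 0.5 percentage points.
- Combined column: 1/(400 + 200) = 1/600 = 0.17 percentage points.

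**How many?** The documents give no C-SSRS positivity rate. Purely as an assumption, let a fraction p of 200 crossovers report a finding for Weeks 12 to 16. The expected count is 200p, and the chance of at least one is 1 − (1 − p)^200:

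- p = 0.25%: 0.5 expected, 39%
- p = 0.5%: 1 expected, 63%
- p = 1%: 2 expected, 87%
- p = 2%: 4 expected, 98%

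These overstate the effect on the table, because a Week 16 finding changes a participant's category only if nothing equal or worse is recorded later in the period.

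**The case against.** The strongest reply is that SAP 4.5 already commits to analysis by treatment actually taken, so that Week 16 is shorthand for the crossover. That is a fair guess at intent. But the principle is general and the window is an explicit inclusion rule, and a programmer following the window will include the record. The group definition also allows crossover later than Week 16, in which case the fixed start brings in further time before the first JNJ-77242113 dose.

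Several other replies stand, in whole or in part:

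- The crossover group is not the only one without a dose anchor. Other groups in the same summary start at the Week 24 randomization, and the withdrawal exclusion starts at Week 28. The contrast with the dose-anchored groups supports the point but does not prove it; the recall period does.
- No sentence says that the C-SSRS is done before the dose. That order is inferred from the dispensing note, which cannot be fully literal because a post-dose PK sample is drawn at the same visit. The C-SSRS point does not need the inference.
- The error runs in the cautious direction: it adds findings to the JNJ columns and cannot hide one.
- Protocol 7.1.3 stops participants with ideation level 4 or 5 or suicidal behavior who are judged at risk, some of them before they would cross over. What can be misassigned is therefore mainly ideation at levels 1 to 3. SAP 4.5.2 also plans a listing of participants with suicidal ideation or behavior.

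A reader might infer that counting the same record under Placebo through Week 16 is a further error. It is not: the summaries are cumulative and overlap, and that placement is correct. Only the later placement under JNJ-77242113 is wrong.

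**Conclusion.** The point holds as a misattribution of limited size. For the summary through Week 52 or the Week 52 lock reporting period, the written window puts a placebo-period C-SSRS recall into two JNJ-77242113 columns, against the SAP's own principle. The share is at most 1 of 8 interviews and 4 of about 40 recalled weeks for a crossover participant who attends every visit to Week 52, and less with later visits. Each misassigned participant is worth 0.5 and 0.17 percentage points in the two columns, assuming that the planned 200 and 400 participants contribute. The number affected cannot be derived from the documents and is probably small.

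Three wider readings are not supported:

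- That the placebo-controlled safety comparison is compromised. The through-Week-16 summary by arm is unaffected, and no formal safety comparison is planned.
- That the Week 160 summary carries the same error. SAP 4.5 describes that summary by exposure to JNJ-77242113 and does not repeat the Week 16 start.
- That the Week 16 ECG is established as a placebo measurement reported as on-drug. It is probably pre-dose, but only by inference from the order of procedures. SAP 4.5.3.6 shows ECG values by scheduled time point, so at most the pooled post-baseline abnormality summary and listing are affected.

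**What to change.** Two wording changes in the SAP:

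1. In 4.5, summary through Week 52, replace the Week 16 start for crossover participants with *at or after the first JNJ-77242113 administration*. This matches the groups already anchored to a dose. It also covers participants who cross over late and any other Week 16 measurement taken before the dose.
2. In 4.5.3.3, add: *For crossover participants in JNJ-77242113 columns, the first post-baseline C-SSRS is the first interview after the visit at which JNJ-77242113 was first administered (normally Week 20).* The first change alone is not enough, because an interview held just after the dose would still recall placebo weeks.

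The cost is one phrase and one sentence, with the matching programming. No new data are needed, and no other analysis changes.
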